9.5 Statistical Analyses

9.5.1 Analysis Populations

The following populations are defined for this study:

Safety Population – The safety population includes all subjects who have been enrolled in the study and injected with Tc 99m tilmanocept regardless of imaging or biopsy status.

Intent-to-Assay (ITA) Population – the ITA population includes all subjects who have been enrolled in the study, injected with Tc 99m tilmanocept, received all imaging procedures, and have been biopsied.

Per-Protocol (PP) Population – the PP population consists of all ITA subjects without major protocol violations. At least 4 evaluable synovial biopsy samples must be available for a subject to be included in the PP population.

9.5.2 Analysis of Baseline and Demographic Characteristics

Baseline and demographic characteristics of the safety population will be summarized. Continuous variables (age, height, weight) will be summarized via mean, standard deviation, minimum, maximum, and number of non-missing responses. Categorical variables (gender, race and ethnicity) will be summarized via counts and percentages.

9.5.3 Analysis of Efficacy Variables

All efficacy analyses will be conducted on both the ITA and PP populations. The ITA population will be the primary analysis set. Additional efficacy analyses may be described in the study SAP.

9.5.3.1 Primary Endpoint

The primary endpoint will be analyzed by computing the Pearson (product-moment) and Spearman (rank) correlation coefficient between the TUV for the biopsied joint and the final CD206 expressing macrophage count. The CD206 expressing macrophage count is derived from IHC histopathology and ultrasound imaging:

- The fraction of CD206 expressing macrophages under 4x and 10x power magnification, defined as the ratio of the total fluorescent stained area to total field area. Specifically, area fraction (AF) is defined as

$$AF = \frac{\text{Total Stained Area}}{\text{Total Field Area}} \times 100\%.$$

- The volume of synovial tissue in the biopsied joint, defined as the ultrasound synovial thickness score (Vol). The CD206 macrophage count will be the product of these 2 variables (that is, $CD206 = AF * Vol$).

CD206 expressing macrophage fraction and TUV_{joint} will be summarized with descriptive statistics (number of data pairs, means, standard deviations, minima, medians, and maxima as well as the Pearson correlation between the variables). The ultrasound synovitis score will be summarized with a frequency table. A 95% confidence interval for the population correlation coefficient (ρ) based on the Fisher Z-transformation (the inverse hyperbolic tangent) and its normal approximation will be provided. The joint distribution of the CD206 macrophage count and TUV_{joint} will be summarized graphically with a scatter diagram of the data pairs with the least-squares regression line superimposed on the graph. The joint distribution of the component variables of CD206 macrophage count will be graphically summarized with box plots showing the conditional distribution of TUV_{joint} for each category of synovitis score.

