	
Primary Efficacy Analysis
 
The primary endpoint will be analyzed by computing the Pearson (product-moment) and Spearman (rank) correlation between the TUV_{joint} for the biopsied joint and 2 measures of macrophage prevalence:
 
• The fraction of CD206-expressing macrophages visible in the microscope field under 4x and 10x power magnification, measured as the area fraction (AF) $AF = \frac{\text{Total Stained Area}}{\text{Total Field Area}} \times 100\%.$ 
• The volume of synovial tissue in the biopsied joint derived from the ultrasound synovitis score (Vol). The final CD206-expressing macrophage count is defined as the product of Vol and AF defined above. 
A 95% confidence interval for the population correlation coefficient measuring the association between TUV and CD206 expression (as measured via IHC) will be computed using the Fisher's Z-transformation method ($Z = \tanh^{-1} r$) and its asymptotic Normal approximation. Statistical summaries of the marginal distributions of TUV_{joint} and CD206 macrophage count will be provided (mean, standard deviation, number of cases, median, and range).
 
Secondary Efficacy Analyses
 
The degree of co-expression of CD68, CD163, and/or CD206 macrophage types will be assessed by calculating the Pearson (product-moment) correlations and Spearman rank correlations among these variables. The marginal distributions will be summarized by calculating the mean, standard deviation, number of cases, median, and range for each variable.
 
The ability of TUV_{joint} to discriminate among lympho-myeloid, diffuse myeloid, and pauci-immune fibroid types will be assessed by fitting a multinomial logistic regression model with RA pathotype as the response variable and TUV_{joint} as the explanatory variable. ROC curves will be generated for the multinomial logistic model using the lympho-myeloid type as the base class. No inferential statistics will be generated for this endpoint.

--	---

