8.5.2 Biopsy Procedure

Subjects will undergo a synovial biopsy of a single joint in the hand or wrist. The synovial biopsy will be performed by a trained member of the clinical study team. Biopsy samples (approximately 12) will be obtained via an 18- or 19-gauge ultrasound-guided quick core biopsy needle and immediately prepared for pathology assessment. Biopsy procedures including subject preparation, tissue harvest, and post-procedure care will be completed in accordance with institutional SOPs.

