8.6 Pathology Evaluation of Synovial Tissue

Following the synovial biopsy, tissue will be collected following local SOPs, processed, and shipped to the central pathology lab in accordance with the NAV3-32 Pathology Manual. If fewer than 4 biopsy samples can be obtained for a given subject, all samples will be used for IHC analyses, but that subject's pathology data will be considered non-evaluable and will be excluded from the PP population. If 4 to 6 biopsy samples are obtained, all samples will be used for IHC analyses, and the subject's pathology data will be included in the PP population. When > 6 biopsy samples are obtained, 4 to 6 of the samples will be used for IHC and the remaining samples will be split approximately evenly to be used for RNA-seq and flow cytometry analyses, when applicable.

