9.3 Efficacy Variables

The primary efficacy variables for this study are defined below:

- Tc 99m tilmanocept uptake values (TUV_{joint}) for the biopsied joints;
- IHC assessment of macrophage expression of the CD206 receptor.

The secondary variables for this study are defined below:

- IHC and immunofluorescence assessment of macrophage expression and co-expression of the CD68 and CD163 receptors;
- Pathotype classification of RA disease as lympho-myeloid, diffuse myeloid, or pauci-immune fibroid, based on TUV_{joint} .

The exploratory efficacy variables for this study are defined below:

- IHC assessment of macrophage expression of the CD3, CD20, CD55, and TE7 biomarkers;
- mRNA levels in synovial tissue for the CD206, CD163, and CD68 biomarkers;
- Flow cytometry measurements of CD206, CD163, and CD68 biomarker expression and co-expression.
- IHC assessment of the expression of a biomarker (e.g., CD206, TE7) is determined from immunofluorescent microscopy, specifically:
 - The ratio of the total fluorescent stained area to the total field area under 4x and 10x power magnification.

All IHC assessments will be done at a single laboratory in accordance with the laboratory SOPs.

- Classification of synovial anatomic pathology into lympho-myeloid, diffuse myeloid, and pauci-immune fibroid types using a multinomial logistic regression model with TUV_{global} as a covariate.
- Tc 99m tilmanocept global uptake values (TUV_{global}) per subject.

It is presumed that the presence of radiotracer uptake for a joint indicates the presence of activated macrophages. The use of the term “localization” is synonymous with radiotracer uptake.

TUV is defined as:

$$TUV_{ROI} = \frac{\bar{X}_{joint}}{\bar{X}_{RR}};$$

where

- \bar{X}_{joint} is the average pixel intensity of a region of interest (ROI) of a subject at the time of imaging (nominally 60 minutes);
- \bar{X}_{RR} is the average pixel intensity of the reference region (RR) of a subject at the time of imaging (nominally 60 minutes).

Calculation of TUV_{joint} and TUV_{global} are further described in the study statistical analysis plan (SAP).

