9.5.3.2 Secondary Endpoints

Co-expression of the CD68, CD163, and CD206 markers will be analyzed by 2 methods. First, by providing the product-moment and Spearman rank correlation matrices of the IHC field measurements (that is, the fraction of macrophages expressing the markers will not be multiplied by the synovitis score). Summary statistics of the data triplets used to calculate the correlation matrices will be provided (number of data triplets, means, standard deviations, minima, medians, and maxima). In the second method, histological sections will undergo immunofluorescent staining for the 3 markers and DAPI. For each section evaluated, up to 50 cells from the synovial sublining will be identified for each of the 3 markers. For each identified cell (up to 150/section), the rate of co-expression of the 3 markers will be determined. For sections with sparse marker expressing cells, four microscope fields will be randomly selected. Co-expression of the markers will be quantified for any cell observed expressing any marker.

The ability of TUV_{joint} to discriminate among lympho-myeloid, diffuse myeloid, and pauci-immune fibroid RA disease types will be evaluated with a multinomial logistic regression

model with TUV_{joint} as a covariate. RA type will be the response variable and TUV_{joint} will be the explanatory variable. ROC curves will be generated using the lympho-myeloid type as the base class. The marginal distribution of disease type will be summarized with a frequency table, while the marginal distribution of TUV_{joint} will be summarized with descriptive statistics (number of data pairs, mean, standard deviation, minimum, median and maximum). The joint distribution will be graphically summarized with box plots showing the conditional distribution of TUV_{joint} for each disease type.

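### The CD206 area fraction is divided by microscope field area, not tissue area, so as written it also depends on how much of the field the biopsy fragment fills

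*Protocol*

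**What the plan says.** Protocol 9.5.3.1 and SAP 4.2.1 describe AF as the fraction of CD206 expressing macrophages, "defined as the ratio of the total fluorescent stained area to total field area", and express it as a percentage. The protocol synopsis gives the same formula. Protocol 9.3 and SAP 4.1.3 extend the denominator to any IHC biomarker: "The ratio of the total fluorescent stained area to the total field area under 4x and 10x power magnification".

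AF is then multiplied by the ultrasound score (Vol): "The CD206 macrophage count will be the product of these 2 variables". This product is correlated with TUV_joint as the primary endpoint. The CD68/CD163/CD206 correlation matrices (Protocol 9.5.3.2, SAP 4.2.2) use AF without Vol.

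On the specimens, Protocol 8.5.2 says: "Biopsy samples (approximately 12) will be obtained via an 18- or 19-gauge ultrasound-guided quick core biopsy needle". On the number used, Protocol 8.6 says: "If 4 to 6 biopsy samples are obtained, all samples will be used for IHC analyses". Subjects with fewer than 4 samples leave the PP population but can remain in the ITA population, which is the primary analysis set.

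The only rule on choosing fields is "For sections with sparse marker expressing cells, four microscope fields will be randomly selected". It belongs to the separate cell-counting method for co-expression, not to AF. Scoring detail is deferred to the Pathology Manual (Protocol 8.6.2) and to the SOPs of a single laboratory (Protocol 9.3). Neither was available for this review.

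**The concern.** A needle fragment from a finger or wrist joint need not fill a low-power field. Where it does not, blank slide enters the denominator, and two joints with the same CD206 staining in their tissue receive different AFs because one gave smaller fragments. Protocol 9.4 ties the final sample size to precision for the correlation of TUV_joint with CD206 macrophage density. A field-based AF measures density only if fill is constant.

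The consequences can run in opposite directions:

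- **Primary correlation.** Fill unrelated to TUV_joint is noise in one variable and pulls the correlation towards zero. There are only 12 to 24 joints to absorb it.
- **Marker matrices.** If markers are scored on equally filled fields, fill is a common factor and pushes their correlations upwards.

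**Working it through.** The plan gives no numerical value for AF, so there is no figure to reproduce. The check is on what the formula implies.

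**1. Identity.** Stained / field = (stained / tissue) × (tissue / field). Write this as AF = D × f, where D is the stained fraction of tissue and f is the fill. With D fixed at 10%, AF is 2.5%, 5%, 7.5% and 10% at fills of 25%, 50%, 75% and 100%. That is a fourfold spread with no change in expression. The other factor, Vol, can differ only 3/2 = 1.5-fold, because biopsied joints must score 2 or 3.

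**2. Effect on the primary correlation.** Let r be the true correlation of TUV_joint with D, and let c_D and c_f be the CVs of D and f. If f is independent of both D and TUV_joint:

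r(TUV, D·f) = r × c_D / √[(1 + c_D²)(1 + c_f²) − 1]

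With Vol independent of the rest and equally likely to be 2 or 3, c_V = 0.5/2.5 = 0.2, and a factor (1 + 0.2²) = 1.04 enters the product under the root.

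**3. Effect on the marker matrices.** For two markers that are truly independent, have equal c_D and share the same f:

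false r = c_f² / [(1 + c_D²)(1 + c_f²) − 1]

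**4. Inputs, all assumed.** r = 0.57 and c_D = 0.5. Three values of c_f are used:

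- 0.14 is what core width alone gives if it is uniform over 0.6 to 1.0 mm: (0.4/√12)/0.8 = 0.14, with coverage close to proportional to width.
- 0.3 and 0.5 stand for added variation from length, folding and placement. The documents give no input for these.
- For scale, fill uniform over 50–100% has c_f = (0.5/√12)/0.75 = 0.19, and over 20–100% it has c_f = (0.8/√12)/0.6 = 0.38.

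| c_f | r with AF | r with AF × Vol | False r, two independent markers |
|---|---|---|---|
| 0 (fields always full) | 0.57 | 0.52 | 0 |
| 0.14 | 0.54 | 0.50 | 0.07 |
| 0.3 | 0.47 | 0.44 | 0.25 |
| 0.5 | 0.38 | 0.36 | 0.44 |

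Example for c_f = 0.3 without Vol: 1.25 × 1.09 − 1 = 0.3625; 0.57 × 0.5/√0.3625 = 0.47; false r = 0.09/0.3625 = 0.25. With Vol: 1.25 × 1.04 × 1.09 − 1 = 0.417; 0.57 × 0.5/√0.417 = 0.44.

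**5. Averaging over samples.** If areas are totalled over 4 to 6 samples per joint and core widths vary independently, c_f falls from 0.14 to about 0.14/√4 = 0.07 or 0.14/√6 = 0.06. Then 0.57 becomes about 0.56.

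These figures are for the Pearson coefficient. The Spearman coefficient, also planned, was not calculated.

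**The case against.** The strongest reply is that the formula is not the whole measurement procedure. Field placement and scoring are left to the Pathology Manual and to one laboratory's SOPs. If those place every field inside tissue, or limit the analysed area to tissue, fill is constant and there is no bias. This stands as a limit on the harm. It does not correct the formula: if the laboratory already uses tissue area, the protocol and SAP misdescribe the primary variable.

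A reader might infer that AF in this trial is certainly distorted by fragment size. The documents do not support that, because they do not show what the laboratory does.

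A reader might also take a 6.25-fold AF difference between magnifications, (10/4)², as a fact from the documents. It needs identical optics at both powers and tissue lying wholly inside the 10x field. For a core running across the field (assumed 22 mm field number, width 0.6 to 1.0 mm), coverage is 14–23% at 4x and 34–56% at 10x, a ratio of about 2.4 to 2.5. A constant ratio would in any case leave both correlation coefficients unchanged within a magnification. How the 4x and 10x values are combined is a separate gap that a tissue denominator does not close.

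Finally, a reader might expect the fall to 0.38, or suppose that thicker synovium gives fuller fragments and inflates the correlation. The first rests on a fill CV of 0.5 for which the documents give no basis; core width alone gives 0.14. The second is possible, but nothing in the documents sizes it.

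**Conclusion.** The point holds as a defect in the written definition. Every statement of AF in the two documents uses field area, and none excludes empty area, so AF as written is the CD206 tissue fraction times fill. Whether this affects the data depends on laboratory rules that were not available.

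Under the assumptions above, the loss in the primary correlation runs from nil (full fields) through about 0.03 (core width only) to about 0.19 (fill CV 0.5, from 0.57 to 0.38). With Vol included, the largest loss is from 0.52 to 0.36. For comparison, at 24 joints the 95% Fisher interval around an observed 0.50 already runs from 0.12 to 0.75, so the milder losses would be hard to see in the result. The study sets no success threshold on the size of r.

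This is a should-fix, to be settled before images are scored. A stronger rating would need evidence that scored fields are in fact unevenly filled.

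**What to change.** In the protocol synopsis, Protocol 9.3 and 9.5.3.1, and SAP 4.1.3 and 4.2.1, define:

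AF = total stained synovial tissue area / total synovial tissue area in the same fields × 100%

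Exclude blank slide, sum numerator and denominator over all IHC sections of the joint, and use the same definition for every IHC marker. Align the Pathology Manual with it. If the laboratory already works this way, the change is to wording only.

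The cost is small but not zero: a tissue mask for images already planned, and a written segmentation rule. Recognising synovial tissue takes histological judgement. The DAPI stain is named only for the co-expression method and H&E is a separate stain, so the rule must say which image supplies the mask. No new sample or patient procedure is needed.

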9.5.3.2 Secondary Endpoints

Co-expression of the CD68, CD163, and CD206 markers will be analyzed by 2 methods. First, by providing the product-moment and Spearman rank correlation matrices of the IHC field measurements (that is, the fraction of macrophages expressing the markers will not be multiplied by the synovitis score). Summary statistics of the data triplets used to calculate the correlation matrices will be provided (number of data triplets, means, standard deviations, minima, medians, and maxima). In the second method, histological sections will undergo immunofluorescent staining for the 3 markers and DAPI. For each section evaluated, up to 50 cells from the synovial sublining will be identified for each of the 3 markers. For each identified cell (up to 150/section), the rate of co-expression of the 3 markers will be determined. For sections with sparse marker expressing cells, four microscope fields will be randomly selected. Co-expression of the markers will be quantified for any cell observed expressing any marker.

The ability of TUV_{joint} to discriminate among lympho-myeloid, diffuse myeloid, and pauci-immune fibroid RA disease types will be evaluated with a multinomial logistic regression

model with TUV_{joint} as a covariate. RA type will be the response variable and TUV_{joint} will be the explanatory variable. ROC curves will be generated using the lympho-myeloid type as the base class. The marginal distribution of disease type will be summarized with a frequency table, while the marginal distribution of TUV_{joint} will be summarized with descriptive statistics (number of data pairs, mean, standard deviation, minimum, median and maximum). The joint distribution will be graphically summarized with box plots showing the conditional distribution of TUV_{joint} for each disease type.

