In recent years, synovial biopsy-enabled studies have greatly increased our understanding of the pathological processes occurring within the inflamed joints of RA patients (Orr 2017). An important finding of these studies has been that the inflammatory cell compositions of RA inflamed joints can vary between patients (Townsend 2014, van de Sande 2016). The biopsy specimens obtained from different RA patients can have different numbers and densities of macrophages and monocytes, lymphocytes and lymphocyte containing structures, and fibroblast-like synoviocytes (Orr 2017). These differences in cellular composition suggest that RA inflammation can be divided into 3 pathotypes, referred to as diffuse myeloid, lympho-myeloid, and fibroid, respectively (Dennis 2014, Astorri 2015). High densities of macrophages can occur in both the myeloid and lymphoid pathotypes, whereas the fibroid pathotype is largely devoid of both macrophages and lymphoid cells. These pathotypes are not fully discrete, with some overlap occurring. However, they provide a strong basis for temporal or cytological compartmentalization in RA disease natural history.

Current studies utilizing IHC analyses of synovial biopsies are insufficient to determine the distribution of the various pathotypes in RA patients but suggest that the diffuse myeloid and lympho-myeloid pathotypes are about equally frequent in RA patients with the fibroid pathotype being less common. There is growing evidence that patients with different RA pathotypes respond differently to various therapies, holding out the possibility that determining the RA pathotype of an individual patient's RA can direct the choice of the most effective therapy for that patient (i.e., personalized RA therapy) (Dennis 2014). This is an area of ongoing active investigation in RA therapy research (Pitzalis 2013, Donlin 2018, Mandelin 2018). However, already there is significant evidence indicating that patients with a myeloid-

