driven RA pathotype and/or with high densities of macrophages in their inflamed synovium respond best to anti-TNF α biologic therapy (Wijbrandts 2008, Dennis 2014), whereas patients with a fibroid pathotype do not respond significantly to anti-TNF α therapy. Although these results need to be confirmed and elaborated upon in further studies, they suggest that determination of the density of activated macrophages in the inflamed synovial membranes of patients with RA could facilitate identification of those RA patients who would most benefit from anti-TNF α therapy and/or those who would not receive benefit. Additional work in this field seeks to determine if similar associations between the efficacies of other treatments and synovial pathotypes can identify those treatments that are most effective in patients with lympho-myeloid and/or fibroid RA pathotypes. Such results, if attained, would provide a great benefit to RA patients by enabling personalized delivery of optimal treatments to all RA patients. The study to be conducted (NAV3-32) is designed to establish the correlation between Tc 99m tilmanocept localization to RA inflamed joints and the number and density of CD206 expressing cells (i.e., macrophages) in the inflamed joints as determined by IHC evaluations of synovial biopsy specimens. If this study is successful, Tc 99m tilmanocept imaging may be able to discriminate the fibroid pathotype from the myeloid and lymphoid pathotypes and may be able discriminate all 3 pathotypes from each other.

Previously generated results from clinical imaging studies conducted by Navidea and extensive peer reviewed scientific literature strongly indicate that Tc 99m tilmanocept can enable non-invasive imaging of aggregates of CD206-expressing cells associated with various pathologies using planar scintigraphy. While it has been suggested that synovial biopsy and IHC evaluations might be translatable to common rheumatological clinical practice, there are 5 reasons why quantitative assessment of CD206 positivity enabled by Tc 99m tilmanocept imaging may be preferred to synovial biopsies for evaluations of RA patients.

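### With lympho-myeloid as base class, no ROC curve is specified for diffuse myeloid versus pauci-immune fibroid, yet the SAP judges three-way discrimination from these curves

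*Protocol*

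**What the plan says.** Protocol 9.5.3.2 says that the ability of TUVjoint to "discriminate among lympho-myeloid, diffuse myeloid, and pauci-immune fibroid RA disease types will be evaluated with a multinomial logistic regression" model, and that "ROC curves will be generated using the lympho-myeloid type as the base class". Protocol 9.5.3.3 says the same for TUVglobal. SAP 4.2.2 and 4.2.3 and the synopsis carry the same base class. None of these places lists the pairs to be plotted. The synopsis adds, for both TUVjoint and TUVglobal, "No inferential statistics will be generated for this endpoint".

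Protocol 1.1 gives the reason for looking at pathotypes:

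- On biology: "High densities of macrophages can occur in both the myeloid and lymphoid pathotypes, whereas the fibroid pathotype is largely devoid" of macrophages and lymphoid cells.
- On aim: "If this study is successful, Tc 99m tilmanocept imaging may be able to discriminate the fibroid pathotype from the myeloid and lymphoid pathotypes". The same sentence adds that all three types may prove separable from one another.
- On therapy: it contrasts patients whose disease is myeloid-driven and/or macrophage-rich, who are said to respond best to anti-TNF treatment, with fibroid patients, who are said not to respond significantly.

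The last paragraph of SAP 4.2.3 sets a rule. If the multinomial ROC curves show that TUVjoint and TUVglobal separate the three types, nothing further is done. If not, two binary logistic regressions of fibroid versus non-fibroid are run, one on TUVjoint and one on TUVglobal. The rule has no numerical criterion.

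**The concern.** The stated aim needs fibroid set against each of the other two types, and its stronger form needs all three pairs. With lympho-myeloid as base, fibroid versus lympho-myeloid and diffuse myeloid versus lympho-myeloid each get a curve. Diffuse myeloid versus fibroid does not.

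This goes beyond display because of the SAP 4.2.3 rule. No inference is planned for these analyses, so the curves carry the conclusion and also decide whether the fibroid regressions are run. If both planned curves look good, the plan allows TUV to be reported as separating three types, with no further analysis, when one pair has not been examined by the stated method.

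**Working it through.** The plan gives no figure to reproduce here. The check is a count, followed by a test of whether the two planned curves fix the third.

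**Count.** Three types give 3 × 2 / 2 = 3 pairs. The base class appears in two of them:

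- diffuse myeloid v lympho-myeloid: curve
- pauci-immune fibroid v lympho-myeloid: curve
- diffuse myeloid v pauci-immune fibroid: no curve

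Coverage is 2 of 3, for TUVjoint and again for TUVglobal.

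**Do the two curves imply the third?** In a baseline-category logit with one explanatory variable, the log odds for any pair is linear in TUV. A pairwise ROC curve is therefore the curve of TUV itself between those two groups. Assume, for illustration only, that TUV is normal within each type. Then

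AUC = Φ( (m₁ − m₂) / √(s₁² + s₂²) ).

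The means and SDs below are assumed, because the documents give none. LM is lympho-myeloid, DM diffuse myeloid, PF pauci-immune fibroid.

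| Case | LM mean, SD | DM mean, SD | PF mean, SD | DM v LM | PF v LM | DM v PF |
|---|---|---|---|---|---|---|
| 1 | 0, 0.2 | 0.721, 1 | −0.721, 1 | 0.76 | 0.76 | 0.85 |
| 2 | 0, 1 | 1, 1 | −1, 1 | 0.76 | 0.76 | 0.92 |
| 3 | 0, 3 | 2.236, 1 | −2.236, 1 | 0.76 | 0.76 | >0.99 |
| 4 | 1.5, 1 | 0, 1 | 0, 1 | 0.86 | 0.86 | 0.50 |

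Case 2: the planned curves give Φ(1/√2) = Φ(0.707) = 0.76, and the unseen pair gives Φ(2/√2) = Φ(1.414) = 0.92. Case 4: the planned curves give Φ(1.5/√2) = Φ(1.061) = 0.86, and the unseen pair gives Φ(0) = 0.50.

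Cases 1 to 3 hold both planned areas at 0.76 while the third runs from 0.85 to above 0.99. Case 4 is the harmful one: both planned curves look good and the unseen pair is not separated at all. It is not a forecast. The biology in Protocol 1.1 would not lead one to expect diffuse myeloid and fibroid joints to have the same uptake. It shows only that the SAP 4.2.3 judgment can be wrong for the pair that is not plotted.

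**Is the contrast lost?** No. The slope for diffuse myeloid v fibroid is the difference of the two fitted slopes. On one simulated data set of 24, with lympho-myeloid as base, the slopes were 1.1085 (DM) and −1.6688 (PF), so the difference is 1.1085 + 1.6688 = 2.7773. Refitting with fibroid as base gave 2.7773 directly. The model already holds the contrast; what is missing is a planned output. The SAP's list of tables has none for the multinomial coefficients.

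**The case against.** Four points can be made for the plan, and each stands in part.

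- **The SAP has a fallback.** The fibroid versus non-fibroid regressions do set diffuse myeloid joints against fibroid. If the two macrophage-rich types prove hard to tell apart, as Protocol 1.1 gives some reason to expect, the rule should send the analysis there. So a reader who infers that diffuse myeloid joints are never compared with fibroid goes too far. The remedy is still partial: it depends on a rule without a criterion, it pools diffuse with lympho-myeloid, and its listed outputs (Tables 57 to 60) are descriptive, with no ROC figure.
- **All three types are displayed elsewhere.** Box plots of TUV by disease type are planned, and Table 50 summarises TUVglobal by type. This is true, but the SAP 4.2.3 judgment is tied to the ROC curves.
- **The ROC construction is not defined.** The SAP writes the model as ln(πⱼ/(1 − πⱼ)), which is category versus rest and not a baseline-category logit. Figures 4 and 5 are titled by disease type. One-versus-rest curves cannot be excluded. A fibroid-versus-rest curve would use the diffuse joints, but would not isolate diffuse versus fibroid either. This is a further reason to name the pairs.
- **The missing pair is not the whole rationale.** A reader might infer that the protocol's case rests on diffuse myeloid versus fibroid alone. It does not. The aim sets fibroid against both other types, the anti-TNF argument covers high macrophage density as well as myeloid-driven disease, and "High densities of macrophages can occur in both the myeloid and lymphoid pathotypes". Fibroid versus lympho-myeloid is part of that case and has its curve. Diffuse versus lympho-myeloid is needed for three-way separation, so that curve is not wasted.

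It is also tempting to ask for fibroid as base class and to claim better precision. The null SE of an area is √((m+n+1)/(12mn)): √(9/192) = 0.22 for 4 v 4 joints and √(13/384) = 0.18 for 4 v 8. The smaller value belongs to a pooled comparison. Pairwise curves against fibroid would still be 4 v 4 at the minimum interim mix, so no gain follows.

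**Conclusion.** The point holds in a limited form. On the pairwise reading, 2 of 3 pairs have an ROC curve. The pair without one is one of the two fibroid contrasts named in Protocol 1.1. The SAP nevertheless draws a three-type conclusion from these curves and may stop there. The planned curves do not determine the missing one: two areas of 0.86 are compatible with 0.50 for the third.

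This rests on reading base class in its usual sense. On a one-versus-rest reading, the pair is still not shown in isolation. The areas are illustrations under assumed normal distributions. The consequence is confined to a secondary and an exploratory descriptive analysis. The primary correlation is untouched, and the contrast can be estimated from the planned model. It is worth correcting because a stated decision rule depends on it and the correction is small.

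**What to change.** - In Protocol 9.5.3.2 and 9.5.3.3, the matching synopsis text, SAP 4.2.2 and 4.2.3, and Figures 4 and 5, specify ROC curves for all three pairs, for TUVjoint and for TUVglobal: diffuse myeloid v lympho-myeloid, fibroid v lympho-myeloid, and diffuse myeloid v fibroid.
- In SAP 4.2.3, base the discrimination judgment on all three curves and state the criterion.
- Reconcile the SAP model equation, which is category versus rest, with the base-class wording, and say how the ROC curves are built from the fit.

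The base class can stay as it is: it does not alter the fit, and once all three pairs are shown it no longer decides what is seen. The cost is one extra curve per figure and a few sentences, with no new data and no change in sample size.
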